8.1 Efficacy assessments

Not applicable.

Page 43 of 82 Version: 4.0 Date: 13 FEB 2023

8.2 Safety assessments

Planned time points for all safety assessments are provided in the SoA (Section 1.3).

8.2.1 Physical examinations

Complete and symptom-orientated physical examinations will be performed at the time points listed in the SoA (Section 1.3).

- A (complete) physical examination will include, at a minimum, assessments of the cardiovascular, respiratory, gastrointestinal, and neurological systems.
- A brief (symptom-directed) physical examination. The brief physical examination includes an overall health judgment. In-depth physical examinations are required if obvious pathological signs are visible or in the case the subject states any signs or symptoms that indicate need for a physical exam based on investigator discretion.

8.2.2 Vital signs, height, and body weight

Vital signs (comprising systolic/diastolic blood pressure, pulse rate, respiratory rate, and oral body temperature) will be assessed at the times given in the SoA (Section 1.3).

Vitals signs measurements should be preceded by at least 5 minutes of rest for the trial subject in a quiet setting without distractions (e.g., television, cell phones).

Vital signs will be measured with trial subjects in seated position.

Systolic/diastolic blood pressure, respiratory rate, and pulse measurements will be assessed with a completely automated device. Manual techniques will be used only if an automated device is not available.

Oral body temperature (in °C or °F) will be measured and recorded to one decimal place. Body temperature will be reported in °C.

Height and body weight will be measured in centimeters and kilograms and recorded at screening.

8.2.3 Electrocardiograms

A standard 12-lead ECG will be recorded at the times given in the SoA (Section 1.3) using an ECG machine that automatically calculates the heart rate and measures PR, QRS, QT, and corrected QT (QTc; according to Bazett) intervals. The ECG should be performed in the standard supine position. All original ECG readings must be kept as source documents.

All ECGs will be judged by the investigator as clinically significant (yes/no); only the abnormal findings, investigator assessment and heart rate will be recorded in the CRF. If a clinically significant finding is identified, refer further to Section 8.5.1.

8.2.4 Clinical laboratory tests

See the SoA footnotes (Section 1.3) for the list of clinical laboratory tests to be performed at the times given in the SoA. Clinical laboratory tests will be performed at a local

Clinical Trial Protocol Trial number: BNT165-01 Page 44 of 82 Version: 4.0 Date: 13 FEB 2023

laboratory. For details of all assessed blood clinical laboratory parameters, see Section 10.3.

All protocol-required clinical laboratory tests must be conducted in accordance with the local laboratory standard. The investigator must review the laboratory report, and document this review with their signature and date of signature.

All laboratory tests with values considered clinically significantly abnormal during participation in the trial should be repeated until the values return to normal or baseline or are no longer considered clinically significant by the investigator or trial Medical Monitor. If such values do not return to normal/baseline within a period of time judged reasonable by the investigator, the etiology should be identified, and the sponsor notified.

If laboratory values from non-protocol-specified laboratory assessments performed at the laboratory require a change in trial subject management or are considered clinically significant by the investigator (e.g., SAE, AE), then the results must be recorded in the CRF.

8.2.5 Viral screening

Viral screens will be performed at the visit given in the SoA (Section 1.3). The viral screen comprises a screen for HIV 1, HIV 2, Hepatitis B, and Hepatitis C. Viral screen testing will be performed at a local laboratory. In addition, nasal or oral swab for rapid SARS-CoV-2 antigen test will also be taken at the visit given in the SoA (Section 1.3).

8.2.6 Subject e-diaries for assessment of reactogenicity (local and systemic reactions)

Subject e-diaries will be issued, trained, and collected by trial site personnel at the visits given in the SoA (Section 1.3).

Subjects will be asked to:

- Report reactogenicity (incl. oral body temperature) daily for 7 d after each IMP dose using an e-diary.
- Report the use of antipyretic/analgesic medication to treat symptoms associated with IMP administration for 7 d after each IMP dose using an e-diary.
- Record the worst grade for each symptom at approximately the same time every evening.
- Contact the site if they experience any severe or potentially life-threatening reactogenicity events.

8.2.6.1 Assessments of intensity for local reactions

Pain (perceived) at the injection site will be assessed as absent, mild, moderate, severe, or potentially life-threatening, according to the grading scale in Table 2.

Erythema/redness and swelling/induration will be measured and recorded in centimeters and then categorized during analysis as absent, mild, moderate, severe or potentially life-threatening, based on the grading scale in Table 2.

Page 45 of 82 Version: 4.0 Date: 13 FEB 2023

Any local reaction of Grade 3 or higher will be confirmed by the investigator along with an assessment if it meets the definition of Grade 4.

Table 2: Local reaction grading scale

	Mild (Grade 1)	Moderate (Grade 2)	Severe (Grade 3) °	Potentially life-threatening (Grade 4) °
Pain at the injection site	Does not interfere with activity	Interferes with activity	Prevents daily activity	Emergency room visit or hospitalization for severe pain
Erythema / redness ^a	2.5 cm to 5.0 cm	>5.0 cm to 10.0 cm	>10 cm	Necrosis or exfoliative dermatitis
Induration / swelling ^b	2.5 cm to 5.0 cm	>5.0 cm to 10.0 cm	>10 cm	Necrosis

- In addition to grading the measured local reaction at the greatest single diameter, the measurement should be recorded as a continuous variable.
- b. Induration/swelling should be evaluated and graded using the actual measurement.
- c. Investigator or medically qualified person confirmation is required.

Source: Based on the US FDA "Toxicity Grading Scale for Healthy Adult and Adolescent Volunteers Enrolled in Preventive Vaccine Clinical Trials".

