8.2.6.2 Assessments of intensity for systemic reactions

Symptoms of systemic reactions will be assessed as absent, mild, moderate, severe, or potentially life-threatening, according to the grading scale in Table 3.

Any systemic reaction of Grade 3 or higher will be confirmed by the investigator along with an assessment if it meets the definition of Grade 4.

Page 46 of 82 Version: 4.0 Date: 13 FEB 2023

Table 3: Systemic reaction grading scale

	Mild (Grade 1)	Moderate (Grade 2)	Severe (Grade 3) ^a	Potentially life-threatening (Grade 4) ^a
Vomiting	1 to 2 times in 24 h	>2 times in 24 h	Requires intravenous hydration	Emergency room visit or hospitalization for hypotensive shock
Diarrhea	2 to 3 loose stools in 24 h	4 to 5 loose stools in 24 h	6 or more loose stools in 24 h	Emergency room visit or hospitalization for severe diarrhea
Headache	Does not interfere with activity	Some interference with activity	Prevents daily routine activity	Emergency room visit or hospitalization for severe headache
Fatigue / tiredness	Does not interfere with activity	Some interference with activity	Prevents daily routine activity	Emergency room visit or hospitalization for severe fatigue
Myalgia – muscle pain	Does not interfere with activity	Some interference with activity	Prevents daily routine activity	Emergency room visit or hospitalization for severe muscle pain
Arthralgia – joint pain	Does not interfere with activity	Some interference with activity	Prevents daily routine activity	Emergency room visit or hospitalization for severe joint pain
Chills	Does not interfere with activity	Some interference with activity	Prevents daily routine activity	Emergency room visit or hospitalization for severe chills
Fever (oral temperature of ≥38.0°C/≥100.4°F)	38.0°C/100.4°F to 38.4°C/101.1°F	38.5°C/101.2°F to 38.9°C/102.0°F	39.0°C/102.1°F to 40.0°C/104.0°F	>40.0°C/>104.0°F

a. Investigator or medically qualified person confirmation is required.

Source: Based on the US FDA "Toxicity Grading Scale for Healthy Adult and Adolescent Volunteers Enrolled in Preventive Vaccine Clinical Trials".

8.2.7 Subject e-diaries for assessment of reactogenicity (local and systemic reactions) – Trial site personnel and investigator tasks

Subject e-diaries will be issued, trained, and collected by trial site personnel at the visits given in the SoA (Section 1.3).

The trial site personnel will ask/remind the trial subjects to:

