8.5.2.1 Solicited local reactions

Local reactions assessed and reported in the e-diary are pain at the injection site, erythema/redness and induration/swelling from Day 1 through Day 7 after trial IMP dose, where Day 1 is the day of IMP injection. A subject is deemed to have had a local reaction if they report the reaction as "yes" on any day (Day 1 through Day 7).

Solicited local reactions will be categorized as mild, moderate, severe or potentially life-threatening) and graded from 1 to 4, as described in Table 4. The categories and grades are based on the FDA Guidance for Industry: "Toxicity Grading Scale for Healthy Adult and Adolescent Volunteers Enrolled in Preventive Vaccine Clinical Trials"⁴.

Any local reaction of Grade 3 or higher will be confirmed by the investigator along with an assessment if it meets the definition of Grade 4.

Page 19 of 36 Version: 3.0 Date: 08 MAY 2024

Table 4: Local reaction grading scale

		Moderate (Grade 2)	Severe (Grade 3) °	Potentially life-threatening (Grade 4) ^c
Pain at the injection site	Does not interfere with activity	Interferes with activity	Prevents daily activity	Emergency room visit or hospitalization for severe pain
Erythema / redness ^a	2.5 cm to 5.0 cm	>5.0 cm to 10.0 cm	>10 cm	Necrosis or exfoliative dermatitis
Induration / swelling ^b	2.5 cm to 5.0 cm	>5.0 cm to 10.0 cm	>10 cm	Necrosis

- In addition to grading the measured local reaction at the greatest single diameter, the measurement will be recorded as a continuous variable.
- b. Induration/swelling should be evaluated and graded using the actual measurement.
- c. Investigator or medically qualified person confirmation is required.

For subjects recording at least one local reaction from Day 1 through Day 7 after IMP injection and for each specific local reaction mentioned in Table 4:

- The maximum severity grade is equal to the highest graded local reaction within the
 recording period. In case of a discrepancy between the subject and investigator
 assessment of severity, the confirmed assessment of the investigator will be used
 for analyses and a comment in the listings will be provided explaining the
 discrepancy.
- Duration will be calculated in days as the difference from the start of the reported event to the resolution of the event, inclusive. If an event resolves and occurs again within the reporting period of the eDiary, the duration will be calculated for each separate event and the maximum duration will be used for the analysis.

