8.5.3 Systemic reactions

The systemic reactions assessed and recorded in the e-diary are vomiting, diarrhea, headache, fatigue/tiredness, Myalgia-muscle pain, Arthralgia-joint pain, chills and fever from Day 1 through Day 7 inclusive, where Day 1 is the day of each IMP injection. The derivations for systemic reactions will be handled similar to the way local reactions are handled for presence of event, severity level, duration, and onset day.

Fever is defined as an oral temperature $\geq 38.0^{\circ}\text{C}$ (100.4°F). Temperatures collected in degrees Fahrenheit will be converted to degrees Celsius using (°F – 32) × 5/9.

Statistical Analysis Plan (SAP) BNT165-01

Page 21 of 36 Version: 3.0 Date: 08 MAY 2024

The highest oral temperature for each day will be recorded in the e-diary and the temperature from Day 1 through Day 7 will be graded as described in Table 5.

Solicited systemic reactions will be categorized as mild, moderate, severe or potentially life-threatening) and graded from 1 to 4 as described in Table 5. The categories and grades are based on the FDA Guidance for Industry: "Toxicity Grading Scale for Healthy Adult and Adolescent Volunteers Enrolled in Preventive Vaccine Clinical Trials"⁴. Any systemic reaction of Grade 3 or higher will be confirmed by the investigator along with an assessment if it meets the definition of Grade 4.

Page 22 of 36 Version: 3.0 Date: 08 MAY 2024

Table 5: Systemic reaction grading scale

	Mild (Grade 1)	Moderate (Grade 2)	Severe (Grade 3) ^a	Potentially life- threatening (Grade 4) ^a			
Vomiting	1 to 2 times in 24 h	>2 times in 24 h	Requires intravenous hydration	Emergency room visit or hospitalization for hypotensive shock			
Diarrhea	2 to 3 loose stools in 24 h	4 to 5 loose stools in 24 h	6 or more loose stools in 24 h	Emergency room visit or hospitalization for severe diarrhea			
Headache	Does not interfere with activity	Some interference with activity	Prevents daily routine activity	Emergency room visit or hospitalization for severe headache			
Fatigue / tiredness	Does not interfere with activity	Some interference with activity	Prevents daily routine activity	Emergency room visit or hospitalization for severe fatigue			
Myalgia - muscle pain	Does not interfere with activity	Some interference with activity	Prevents daily routine activity	Emergency room visit or hospitalization for severe muscle pain			

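### The only mandatory investigator re-check of diary reactions starts at Grade 3 and then overrides the subject's grade, so systematic corrections to the Grade ≥3 proportion run mainly downward, even for redness and swelling graded from a measured diameter

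*Protocol*

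**What the plan says.** Three rules meet here.

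- **Who is checked.** Protocol 8.2.6.1: "Any local reaction of Grade 3 or higher will be confirmed by the investigator". Protocol 8.2.6.2: "Any systemic reaction of Grade 3 or higher will be confirmed by the investigator". SAP 8.5.2.1 and 8.5.3 repeat both. Neither document requires an investigator grade for diary entries of Grade 0 to 2.
- **Whose grade is analysed.** SAP 8.5.2.1: "In case of a discrepancy between the subject and investigator" assessments of severity, "the confirmed assessment of the investigator will be used", with an explanatory comment in the listings. SAP 8.5.3 extends this: "The derivations for systemic reactions will be handled similar to the way local reactions are handled", and severity is among the derivations it names.
- **How redness and swelling are graded.** Protocol 8.2.6.1: "Erythema/redness and swelling/induration will be measured and recorded in centimeters and then categorized during analysis". Table 2 sets Grades 1 to 3 by diameter (Grade 3 is above 10 cm). Grade 4 is a clinical finding: necrosis for swelling, necrosis or exfoliative dermatitis for redness. Footnote c of the same table asks for confirmation of Grades 3 and 4.

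The result affected is the Grade ≥3 line of the reactogenicity overview (SAP 8.5.2.1), given per injection and overall. Protocol 9.4.2 lists it under subject-reported reactogenicity.

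**The concern.** Entries are selected for review because they are high, and the reviewer's grade then replaces them. A Grade 3 entry that was too high is looked for and can be taken out of the count. A Grade 2 entry that was too low is not looked for in the same way. Verification is thus one-sided on a severity summary of the primary objective, in a trial that describes reactogenicity at three dose levels with 16 vaccinees each.

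Redness and swelling raise a second issue. If the category comes from recorded centimetres, a diameter above 10 cm is Grade 3. Under the SAP rule the same record can be tabulated lower because the investigator graded it differently. Apart from that general rule, neither document says which prevails, so two programmers could produce different counts. The investigator may also not see the peak: scheduled site visits fall about 24 h after Doses 1 and 2 and then at 7 d, and after Dose 3 there is none before 7 d.

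**Working it through.** **The plan's own figures.** The documents give no number for this point. Their only design figures, the chance of at least one AE among 20 subjects, reproduce (1 − 0.90^20 = 87.8%; 1 − 0.85^20 = 96.1%) but do not enter here.

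**Step 1: which moves are possible.** Take subject and investigator grades from 0 to 4, which gives 25 pairs, and count those that cross the Grade ≥3 cut.

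- If only subject grades of 3 or 4 are reviewed, 2 subject grades × 3 lower investigator grades (0, 1, 2) = 6 pairs leave the Grade ≥3 group and 0 enter. Changes between 3 and 4 do not matter.
- If the SAP sentence is applied to any discrepancy, as its wording allows, 6 pairs leave and 3 × 2 = 6 enter.

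The mandatory check supplies only the first kind. The second depends on a discrepancy arising by another route.

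**Step 2: weight of one subject.** Each cohort has 16 vaccinees (protocol 4.1.1), so one re-graded subject is 1/16 = 6.25 points. In the combined placebo group it is 1/(3 × 4) = 1/12 = 8.3 points. SAP 8.5.2.1 drops subjects with no diary data, so denominators can be smaller and the step larger.

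**Step 3: illustration on assumed inputs.** None of these inputs is in the documents. Let p be the true Grade ≥3 rate, s the share of true cases the diary catches, and f the diary's false-positive rate. Assume the investigator is always right and, as the extreme case, that no upward route is used.

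- Uncorrected diary: p·s + (1 − p)·f
- Check at Grade ≥3 only: p·s
- Check at all grades: p

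| p | s | f | Diary | Check ≥3 only | Check all |
|---|---|---|---|---|---|
| 10% | 80% | 2% | 9.8% | 8.0% | 10% |
| 10% | 80% | 5% | 12.5% | 8.0% | 10% |
| 10% | 90% | 2% | 10.8% | 9.0% | 10% |
| 10% | 90% | 5% | 13.5% | 9.0% | 10% |
| 20% | 80% | 2% | 17.6% | 16.0% | 20% |
| 20% | 80% | 5% | 20.0% | 16.0% | 20% |
| 20% | 90% | 2% | 19.6% | 18.0% | 20% |
| 20% | 90% | 5% | 22.0% | 18.0% | 20% |

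The one-sided check is below the truth in every row, by 1 to 4 points. It is not always the worse figure. In row 4 the diary is 3.5 points too high and the one-sided check 1.0 too low; in row 6 the diary is exact and the one-sided check 4.0 too low. Which is closer depends on error rates that the trial does not know, which argues for showing both.

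**Step 4: effect across dose levels.** If a constant share d of Grade ≥3 reports is downgraded, each proportion is multiplied by (1 − d). Absolute differences between dose levels shrink by that factor; ratios do not change.

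**The case against.** The strongest reply is that the rule is not one-way. The override sentence sets no grade floor and no direction. Investigators review all diary data daily. Protocol 8.2.7 has a subject call about a potential Grade 3 reaction, so the trigger is not tied to the grade in the diary. Necrosis or exfoliative dermatitis makes a reaction Grade 4 at any diameter. All of this stands. A reader might infer that corrections can only lower the proportion, and the documents do not support that. What remains is that none of these routes is a systematic search for under-graded entries.

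Second, a lower figure need not be an understated one: removing a mis-graded Grade 3 entry is a correct change. This also stands. Any bias comes from unequal searching, not from downgrading as such.

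Third, protocol 8.2.7 reserves confirmation of Grades 3 and 4 for recording in the EDC system to an investigator or medically qualified person. For pain and systemic symptoms, analysing the confirmed grade is therefore in line with the protocol. This stands, and the fix keeps that grade. It does not settle redness and swelling. Protocol 8.2.6.1 contains both the centimetre rule and the confirmation, and the two agree if confirming means checking the measurement. The SAP sentence, however, lets a differing grade prevail whatever was measured.

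Fourth, a late look at the arm is not inevitable: subjects must contact the site at once, and ad hoc and unscheduled visits are allowed. This is fair; they are possible but not required for grading.

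Fifth, discrepancies will be explained in the listings, so the subject-reported count could be rebuilt by hand. That is true, but the tabulated proportion would still rest on the override alone.

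**Conclusion.** The point holds in a limited form. The one mandatory re-check begins at Grade 3 and its result replaces the subject's grade, so systematic corrections to the Grade ≥3 proportion run mainly downward. For redness and swelling, the override can place a recorded diameter above 10 cm below Grade 3, which does not fit the protocol's rule of categorising the measurement at analysis.

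The size is unknown. The firm figure is 6.25 points per re-graded vaccinee at 16 per cohort; the 1-to-4-point shortfalls above rest wholly on assumed error rates and on no upward route being used. A reader might infer that severe reactogenicity is understated by a known amount, or that the dose-response is flattened. The documents support neither: they give no re-grading rate, a downgrade may be right, and a constant rate leaves ratios between dose levels unchanged. No formal comparison is affected, because none is planned.

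**What to change.** Amend SAP 8.5.2.1 and 8.5.3; no change to trial conduct is needed.

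1. **Redness and swelling.** Derive Grades 1 to 3 from the recorded diameter. Let the investigator's assessment change the grade only for Grade 4 or for a documented entry or measurement error.
2. **Pain and systemic reactions.** Keep the confirmed grade as planned. Beside it, tabulate Grade ≥3 as reported by the subject, with entry errors removed, and give the number of subjects re-graded up and down per dose level.

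Both grades are already needed for the planned listing comment, so nothing new has to be collected. The cost is SAP wording and one extra row per reactogenicity table. The downside for the sponsor is that the Grade ≥3 figure may come out slightly less favourable.

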8.2.6.2 Assessments of intensity for systemic reactions

Symptoms of systemic reactions will be assessed as absent, mild, moderate, severe, or potentially life-threatening, according to the grading scale in Table 3.

Any systemic reaction of Grade 3 or higher will be confirmed by the investigator along with an assessment if it meets the definition of Grade 4.

Page 46 of 82 Version: 4.0 Date: 13 FEB 2023

Table 3: Systemic reaction grading scale

	Mild (Grade 1)	Moderate (Grade 2)	Severe (Grade 3) ^a	Potentially life-threatening (Grade 4) ^a
Vomiting	1 to 2 times in 24 h	>2 times in 24 h	Requires intravenous hydration	Emergency room visit or hospitalization for hypotensive shock
Diarrhea	2 to 3 loose stools in 24 h	4 to 5 loose stools in 24 h	6 or more loose stools in 24 h	Emergency room visit or hospitalization for severe diarrhea
Headache	Does not interfere with activity	Some interference with activity	Prevents daily routine activity	Emergency room visit or hospitalization for severe headache
Fatigue / tiredness	Does not interfere with activity	Some interference with activity	Prevents daily routine activity	Emergency room visit or hospitalization for severe fatigue
Myalgia – muscle pain	Does not interfere with activity	Some interference with activity	Prevents daily routine activity	Emergency room visit or hospitalization for severe muscle pain
Arthralgia – joint pain	Does not interfere with activity	Some interference with activity	Prevents daily routine activity	Emergency room visit or hospitalization for severe joint pain
Chills	Does not interfere with activity	Some interference with activity	Prevents daily routine activity	Emergency room visit or hospitalization for severe chills
Fever (oral temperature of ≥38.0°C/≥100.4°F)	38.0°C/100.4°F to 38.4°C/101.1°F	38.5°C/101.2°F to 38.9°C/102.0°F	39.0°C/102.1°F to 40.0°C/104.0°F	>40.0°C/>104.0°F

a. Investigator or medically qualified person confirmation is required.

Source: Based on the US FDA "Toxicity Grading Scale for Healthy Adult and Adolescent Volunteers Enrolled in Preventive Vaccine Clinical Trials".

8.2.7 Subject e-diaries for assessment of reactogenicity (local and systemic reactions) – Trial site personnel and investigator tasks

Subject e-diaries will be issued, trained, and collected by trial site personnel at the visits given in the SoA (Section 1.3).

The trial site personnel will ask/remind the trial subjects to:

- Record the worst grade for each symptom in the e-diary at approximately the same time every evening on the day of IMP injection and then every day in the evening for a total of seven consecutive days.
- Measure their body temperature using the provided device and record their body temperature in the e-diary every day including the day of IMP injection.
- To assess any solicited local reactions at the injection site as described in Section 8.2.6.1 and solicited systemic reactions as described in Section 8.2.6.2.
- To contact the site immediately in case of severe or potentially life-threatening reactogenicity events.

Clinical Trial Protocol Trial number: BNT165-01 Page 47 of 82 Version: 4.0 Date: 13 FEB 2023

Investigators will review subject-reported e-diary data at the times given in the SoA (Section 1.3).

Only an investigator or medically qualified person is able to confirm Grade 3 or a potentially life-threatening Grade 4 event for recording in the EDC system.

If a trial subject experiences confirmed Grade 4 reactogenicity, the investigator must immediately notify the sponsor and, if it is determined to be related to the administration of IMP, further IMP administration will be discontinued in that trial subject (see Section 7.1).

If a trial subject experiences a potential Grade 3 reactogenicity or higher, the subject must immediately notify the investigator or some other medically qualified person, who will then confirm the grading, the confirmed Grade 4 reactogenicity will be recorded by the investigator as an SAE. Data for solicited Grade 3 or lower events do not need to be reported separately by the investigator as AEs in the EDC system, unless they are reported as an unsolicited event or extends beyond the 7 d.

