8.2.8 Assessment of local reactogenicity - Investigator tasks

Investigators will assess acute local reactogenicity at the visits given in the SoA (Section 1.3).

Investigators will grade and record acute local reactions as described in Section 8.2.6.1. If any acute local reactions meet any SAE criteria, they must be recorded as an SAE.

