10.4.2 Definition of SAE

A SAE is defined as any untoward medical occurrence that, at any dose:

- Results in death
- Is life-threatening

The term "life-threatening" in the definition of "serious" refers to an event in which the trial subject was at risk of death at the time of the event. It does not refer to an event, which hypothetically might have caused death, if it were more severe.

- Requires hospitalization or prolongation of existing hospitalization:
 - In general, hospitalization signifies that the trial subject has been detained (usually involving at least an overnight stay) at the hospital or emergency ward for observation and/or treatment that would not have been appropriate in the physician's office or outpatient setting. Complications that occur during hospitalization are AEs. If a complication prolongs hospitalization or fulfills any other serious criteria, the event is serious. When in doubt as to whether "hospitalization" occurred or was necessary, the AE should be considered serious.
 - Hospitalization for elective treatment of a pre-existing condition that did not worsen from baseline is not considered an AE.
- Results in persistent disability/incapacity:
 - The term disability means a substantial disruption of a person's ability to conduct normal life functions.
 - This definition is not intended to include experiences of relatively minor medical significance such as uncomplicated headache, nausea, vomiting, diarrhea, influenza, and accidental trauma (e.g., sprained ankle) which may interfere with or prevent everyday life functions but do not constitute a substantial disruption.
- Is a congenital anomaly or birth defect.
- · Other situations:
 - Medical or scientific judgment should be exercised in deciding whether SAE reporting is appropriate in other situations such as important medical events that may not be immediately life-threatening or result in death or hospitalization but may jeopardize the trial subject or may require medical or surgical treatment to prevent one of the other outcomes listed in the above definition. These events should usually be considered serious. Examples of such events include invasive or malignant cancers, intensive treatment in an emergency room or at home for allergic bronchospasm, blood dyscrasias or convulsions that do not result in hospitalization, or development of drug dependency or drug abuse.

Clinical Trial Protocol Trial number: BNT165-01 Page 69 of 82 Version: 4.0 Date: 13 FEB 2023

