10.4.2.1 Use of the terms "severe" and "serious"

The terms "severe" and "serious" are not synonymous. Severity refers to the intensity of an AE (e.g., rated as mild, moderate severe or potentially life-threatening, as described in the US FDA "Toxicity Grading Scale for Healthy Adult and Adolescent Volunteers Enrolled in Preventive Vaccine Clinical Trials"); see Section 10.4.3 for guidance on the assessment of severity; the event itself may be of relatively minor medical significance (such as severe headache without any further findings).

Severity and seriousness need to be assessed independently for each AE recorded on the CRF.

SAEs must be reported by the investigator to the sponsor within 24 h after learning of the event; see Section 10.4.4 for reporting instructions.

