8.5.4 Adverse events

All AEs will be recorded from Visit 1 (Dose 1) until 28 days after each dose; only unsolicited AEs starting after the first IMP administration will be collected. SAEs will be collected from date of informed consent and throughout the whole trial (i.e., until Visit 14). Medically attended adverse events (MAAE) will be collected until 28 d after each dose.

Solicited AEs (i.e., reactogenicity events) are recorded in the trial subjects' e-diaries and should not be reported as AEs unless the solicited AE meets criteria for an SAE or continue past Day 7 of each IMP dose.

Page 23 of 36 Version: 3.0 Date: 08 MAY 2024

All AEs will be coded using the most recent version of MedDRA® coding system version 25.1 or later and graded for severity using FDA Guidance for Industry: "Toxicity Grading Scale for Healthy Adult and Adolescent Volunteers Enrolled in Preventive Vaccine Clinical Trials"⁴. In case a subject has an AE with missing relationship status, the event will be assumed to be related. No imputation for missing grades will be performed.

If an AE is reported more than once by the same subject for a System Organ Class (SOC) / Preferred Term (PT) the associated AE will be counted once for the SOC / PT under the maximum severity.

All AE summary tables will be sorted alphabetically by SOC and PT within SOC.

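### Protocol 8.2.7 makes every confirmed Grade 4 solicited reaction an SAE on grade alone, against the protocol's own seriousness rules, and such events enter the primary SAE proportion

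*Protocol*

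**What the plan says.** Protocol 8.2.7 covers solicited reactions reported in the e-diary. Once the investigator has confirmed the grading, "the confirmed Grade 4 reactogenicity will be recorded by the investigator as an SAE". The confirmation step in 8.2.6.1 and 8.2.6.2 concerns the grade, not seriousness.

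Tables 2 and 3 define Grade 4. For fever it is ">40.0°C/>104.0°F", with no duration. For headache it is "Emergency room visit or hospitalization for severe headache", and diarrhea, fatigue, myalgia, arthralgia and chills follow the same pattern. For injection-site pain it is "Emergency room visit or hospitalization for severe pain".

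Other sections keep grade and seriousness apart:
- Protocol 10.4.2.1: "Severity and seriousness need to be assessed independently for each AE recorded on the CRF".
- Protocol 10.4.2, on the life-threatening criterion: "It does not refer to an event, which hypothetically might have caused death, if it were more severe".
- Protocol 10.4.3: an event is serious if it meets at least one listed criterion, whatever its intensity.
- SAP 8.5.4: solicited events "should not be reported as AEs unless the solicited AE meets criteria for an SAE" or last beyond Day 7.

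The proportion of subjects with at least one SAE is a primary estimand (Protocol 3, SAP 3.1). SAP 8.5.4.1 counts any recorded SAE and does not ask why it was recorded as one.

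**The concern.** Section 8.2.7 turns an intensity grade into a seriousness classification, which 10.4.2.1 and 10.4.3 say must not happen. A reaction can reach Grade 4 without meeting any seriousness criterion. Under 8.2.7 it is still recorded as an SAE and enters the primary SAE proportion.

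That proportion would then combine events that meet the SAE definition with events that only reached a grade. If the investigator also judges the event related, it enters the related-SAE rows of SAP 8.5.4.1 and 8.5.4.2, and it falls under the expectedness assessment that Protocol 8.3.4 applies to related SAEs. With 16 vaccinees per dose level, one event is visible in the result.

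**Working it through.** **1. The plan's own figures.** The documents state no SAE rate and no Grade 4 rate. Their only probabilities are those for seeing at least one AE among 20 subjects (Protocol 9.2, SAP 6). These reproduce: 1 − 0.90^20 = 87.8% (stated 88%) and 1 − 0.85^20 = 96.1% (stated 96%). Nothing below depends on them.

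**2. One event under each rule.** Take a confirmed oral temperature of 40.1°C after a dose, which resolves within the e-diary period and meets no criterion in 10.4.2.

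| Source | Classification |
|---|---|
| Protocol Table 3 | Grade 4 (Grade 3 ends at 40.0°C; no duration needed) |
| Protocol 8.2.7 | SAE |
| Protocol 10.4.2 | Not an SAE: no death, actual risk of death, hospitalization, disability or congenital anomaly, and not judged an important medical event |
| Protocol 10.4.2.1, 10.4.3 | Grade does not decide seriousness |
| SAP 8.5.4 | Not even an AE-page entry: no SAE criterion met, not ongoing past Day 7 |

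**3. Does another section reconcile them?** Protocol 10.4.2.2 is the stated modification of the SAE definition, and it only removes events. Elsewhere the protocol treats high-grade events and SAEs as distinct. Section 7.1 provides a form for SAEs and for Grade 3 or 4 AEs. Section 8.3.2 puts possibly related Grade 3 or higher events on the SAE timeline without calling them SAEs. Section 7.1.1 lists related SAEs, related Grade 4 AEs and fever above 40.0°C lasting over 6 h as separate pausing triggers. No section adds Grade 4 reactions to the definition.

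**4. Effect on the primary proportion.** Planned vaccinees per dose level: 16 (Protocol 9.2). Solicited reactions arise within 7 days of a dose, so they lie inside the SAE window. Exact (Clopper-Pearson) 95% limits, for one such vaccinee with no other SAE and no SAE in the rest of the group:
- by the 10.4.2 criteria: 0/16 = 0% (0% to 20.6%);
- by 8.2.7: 1/16 = 6.25% (0.2% to 30.2%).

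**5. How often.** The documents cannot answer this. Purely as an assumption, let p be the chance that a vaccinee has such a reaction over the three doses, with p from 0.5% to 5%. The chance of at least one is 1 − (1 − p)^n:
- n = 16: 1 − 0.995^16 = 7.7% to 1 − 0.95^16 = 56.0%;
- n = 3 × 16 = 48: 1 − 0.995^48 = 21.4% to 1 − 0.95^48 = 91.5%.

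**The case against.** The best defence is that automatic SAE status is a deliberate, cautious convention for a first-in-human vaccine. Grade 4 is labelled potentially life-threatening, and 10.4.3 associates it with urgent intervention. This is plausible, but the protocol does not say it, and its definition and the SAP say otherwise.

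The defence does limit how far the point can be taken. A reader might infer any of the following, and the documents do not support them:

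- **That sites will classify the same event differently.** Section 8.2.7 is mandatory and, followed as written, leaves sites no choice. Section 8.2.8 ("If any acute local reactions meet any SAE criteria, they must be recorded as an SAE") is not a rival rule: it covers only acute local reactions up to 1 h after dosing and states a sufficient condition, not an only-if.
- **That emergency-room cases are generally non-serious.** Section 10.4.2 counts detention in an emergency ward as hospitalization, treats doubtful hospitalization as serious, and allows judgment on important medical events. Many such cases would qualify.
- **That these events are hidden.** SAP 8.5.2.1 and 8.5.3 already tabulate Grade 4 solicited reactions, and 8.5.4.4 flags solicited events in the AE listings. A reader can trace them. However, the overview row in 8.5.4.1 pools reactions that are SAEs with those lasting beyond 7 days, and the SAE proportion itself is not split.
- **That contamination rises with dose, or that each event becomes a related SAE.** Protocol 4.3 reports dose-dependent reactogenicity for a related vaccine in general, not for Grade 4 events. Relatedness is judged separately (10.4.3).

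A further caution concerns the remedy. The SAE pausing trigger in 7.1.1 admits relatedness assessed by the sponsor. The Grade 4 trigger names the investigator, or absence of an alternative cause. The latter limb may already cover most cases, but the wording differs, so a change of SAE status could affect pausing.

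**Conclusion.** The contradiction between Protocol 8.2.7 on one side and Protocol 10.4.2, 10.4.2.1, 10.4.3 and SAP 8.5.4 on the other stands, and it reaches a primary estimand. Its size is 6.25 percentage points per affected vaccinee at a dose level. This assumes 16 vaccinees, a confirmed Grade 4 reaction that meets no 10.4.2 criterion, and no other SAE in that subject. Transient fever above 40.0°C is the clear example.

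It would go too far to conclude that the trial's serious-risk signal will be overstated. That needs such an event to occur, and the documents give no rate. The analysis is descriptive with no hypothesis tested, so no formal decision rests on the proportion. The defect is an ambiguous primary quantity that is cheap to settle in advance.

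**What to change.** 1. **Protocol.** The sponsor should reconcile 8.2.7 with 10.4.2, 10.4.2.1 and 10.4.3, and with SAP 8.5.4, so that one rule decides when a solicited Grade 4 reaction is an SAE. The effect on the pausing triggers in 7.1.1 must be checked at the same time, and the immediate notice to the sponsor in 8.2.7 kept. No view is taken here on which reporting rule is right.
2. **SAP 8.5.4.1.** Report the primary SAE proportion for events that meet a 10.4.2 criterion. Show SAEs recorded solely because of Grade 4 on a separate line. This keeps the primary quantity well defined whichever reporting rule the sponsor chooses.

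The cost is one recorded seriousness criterion for each of what should be rare events, and one additional table line.
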